**Version Number: v1.0**

**17 April 2024**

## STATEMENT OF COMPLIANCE

The trial will be conducted in accordance with International Conference on Harmonisation Good Clinical Practice (ICH GCP) and applicable United States (US) Code of Federal Regulations (CFR). The Principal Investigator will assure that no deviation from, or changes to, the protocol will take place without prior documented approval from the Institutional Review Board (IRB), except where necessary to eliminate an immediate hazard(s) to the trial subjects. All personnel involved in the conduct of this study have completed Human Subjects Protection and ICH GCP Training.

The protocol, informed consent form(s), recruitment materials, and all subject materials will be submitted to the local Institutional Review Board (IRB) for review and approval. Approval of both the protocol and the consent form must be obtained before any subject is enrolled. Any amendment to the protocol will require review and approval by the IRB before the changes are implemented to the study. All changes to the consent form will be IRB approved; a determination will be made regarding whether a new consent needs to be obtained from subjects who provided consent, using a previously approved consent form.

## 1 PROTOCOL SUMMARY

### 1.1 SYNOPSIS

Title:	WeExPAnd: PrEP Demonstration Project Among Women at Risk for HIV Infection - Preexposure Prophylaxis (PrEP)
Study Description:	This is a prospective, mixed-methods pilot demonstration study using a pre-/post-intervention design to assess the feasibility, acceptability, and preliminary impact of a culturally adapted patient-provider communication tool on PrEP uptake among cisgender women receiving care at federally qualified health centers (FQHCs) in Alabama. The study employs an iterative implementation process guided by the Exploration, Preparation, Implementation, and Sustainment (EPIS) framework and Dynamic Adaptation Process (DAP).
Objectives:	Primary: To assess the feasibility, acceptability, and preliminary impact of an adapted patient-provider communication intervention on PrEP uptake among cisgender women Secondary: To evaluate PrEP medication adherence and clinic visit adherence
Endpoints:	Primary: PrEP uptake rates, intervention feasibility metrics (recruitment numbers, enrollment rate (proportion of eligible participants consenting), participant retention (proportion completing 3-month follow-up), PrEP referral acceptance rate, and intervention delivery completion rate), and intervention acceptability measures (patient satisfaction surveys) Secondary: PrEP adherence (self-report via Visual Analogue Scale), clinic visit adherence (attendance rates)
Study Population:	Cisgender, HIV-uninfected women aged 18 years or older who are English-speaking and report sexual activity or anticipate sexual activity within 6 months.
Phase:	N/A

Description of Study Intervention:	Participants receive a brief patient-provider communication intervention using an adapted flip-book communication tool, optionally preceded by a 3-minute PrEP informational video. The intervention facilitates structured conversations about HIV risk assessment and PrEP as a prevention option, with referrals to PrEP services for interested participants.
Study Duration:	Approximately 18 months for enrollment and intervention implementation, with a 12-month follow-up for outcome assessment
Subject Duration:	Up to 3 months active participation (baseline assessment, intervention visit, 3-month follow-up), with medical record data abstraction at 3 months and 12 months post-intervention

## 1.2 SCHEDULE OF ACTIVITIES (SOA)

Study Activity	Screening	Baseline (Day 0)	Intervention Visit	3-Month Follow-up	12-Month Data Collection
Eligibility Assessment	x				
Informed Consent		x			
Demographics		x			
Baseline Assessments*		x			
PrEP Video (optional)			x		
Patient-Provider Communication Tool			x		
PrEP Referral (if interested)			x		
Patient Satisfaction Survey			x		
3-Month Assessments**				x	
Qualitative Interview				x	

Medical Record Abstraction***				x	x
Adverse Event Assessment		x	x	x	

Notes:

\*Baseline Assessments include: intimate partner violence, depression, anxiety, substance use, sexual behaviors, HIV knowledge, PrEP awareness, social support, spirituality/religiousness, PTSD screening

\*\*3-Month Assessments include: depression, anxiety, substance use, sexual behaviors, HIV knowledge, intimate partner violence, PrEP adherence (if applicable), stage of change

\*\*\*Medical record data abstraction includes PrEP initiation and clinic visit attendance

## 2 INTRODUCTION

### 2.1 STUDY RATIONALE

Cisgender women, particularly women of color living in the rural southeastern United States, remain persistently at risk for HIV infection. Pre-exposure prophylaxis for HIV (PrEP) is a highly effective HIV prevention tool that may overcome barriers experienced by women when using traditional HIV prevention tools, such as condoms, which are primarily used and controlled by male partners. However, we know very little about how to facilitate effective access and use of PrEP for women at high risk for HIV infection. This project seeks to understand how to make PrEP more accessible to these women, which may ultimately affect HIV incidence in this population.

Suboptimal healthcare provider communication about sexual health, HIV/STI risk, and preventive measures like PrEP represents a significant barrier to widespread PrEP uptake. Provider awareness of PrEP for women and willingness to prescribe PrEP to patients is alarmingly low. A collaborative effort among providers and PrEP-eligible women is needed to develop culturally tailored interventions supporting PrEP uptake among women at risk of HIV infection.

### 2.2 BACKGROUND

Despite representing a minority of the US female population, African American (AA) women bear a disproportionate burden of new HIV diagnoses among women each year. These disparities are especially glaring in the Southeast where HIV prevalence and incidence is among the highest in the nation.

Traditional HIV prevention efforts, such as abstinence-only education approaches prevalent in the rural South, have failed to reduce rates of STI and HIV infections. Interventions promoting condom use, partner-based testing, and/or monogamous relationships are dependent on behaviors of women's sexual partners and, therefore, may be outside each woman's direct control. Women experiencing financial challenges may be financially dependent on male partners; they may also be experiencing intimate partner violence, further complicating their ability to make independent sexual health decisions.

Although PrEP can curb incident HIV infection among high-risk individuals, research on its promotion and use among women – particularly in the US South – is limited. Multiple studies indicate that, regardless of geographic location, women as well as staff members at healthcare clinics are unfamiliar with PrEP as an HIV prevention tool and express concern about the broad lack of awareness of its availability to women. However, women, particularly women of color, expressed being generally interested in using PrEP if available, especially if recommended by a trusted healthcare provider.

### 2.3 RISK/BENEFIT ASSESSMENT

#### 2.3.1 KNOWN POTENTIAL RISKS

It is unlikely that patient participants will be at any risk for physical harm because of study participation. Participants may find some of the questions covered in the assessments to be emotionally upsetting.

Participating in qualitative interviews may also be distressing, as the interview may involve discussing personal matters. The most common risks for providers include asking patients uncomfortable sexual health questions.

### 2.3.2 KNOWN POTENTIAL BENEFITS

The potential benefits of the research include improved service delivery, which aims to maximize benefits for patients and minimize adverse health effects. Participants may benefit from receiving information about PrEP as well as referrals to appropriate services if needed.

## 3 STUDY DESIGN

### 3.1 OVERALL DESIGN

This is a prospective, mixed-methods pilot demonstration study using a pre-/post-intervention design to assess the feasibility, acceptability, and preliminary impact of a culturally adapted patient-provider communication tool on PrEP uptake among cisgender women receiving care at federally qualified health centers (FQHCs) in Alabama. The study employs an iterative implementation process guided by the Exploration, Preparation, Implementation, and Sustainment (EPIS) framework and Dynamic Adaptation Process (DAP).

Following formative qualitative research with patients and providers (Phase 1), this protocol focuses on Phase 2 implementation activities. Enrollment occurs in iterative cycles with continuous feedback from an Implementation Resource Team (IRT) to refine the intervention throughout the study period. The study uses a single-arm design without randomization, as this is a pilot feasibility study evaluating intervention implementation rather than comparative effectiveness.

## 4 STUDY POPULATION

### 4.1 INCLUSION CRITERIA

Cisgender women; age 18 years or older; HIV-uninfected according to self-report; report any sex with male partners in the past 6 months OR anticipate sexual activity with male partners in the next 6 months; primary language English; willing and able to give informed consent; receiving care at one of the participating clinic study sites.

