## 5 STUDY INTERVENTION

### 5.1 STUDY INTERVENTION(S) ADMINISTRATION

#### 5.1.1 STUDY INTERVENTION DESCRIPTION

The study intervention consists of a brief patient-provider communication session using a culturally adapted flip-book communication tool, optionally preceded by a 3-minute PrEP informational video. The intervention facilitates structured conversations about HIV risk assessment and PrEP as a prevention option.

During the intervention visit, participants may first watch the informational video about PrEP. The trained study provider then follows up on video content and uses the flip-book communication tool to guide discussion about HIV risk, PrEP candidacy, and prevention options. The session concludes with referral to PrEP services for interested participants or discussion of alternative risk-reduction strategies for those not interested in PrEP.

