## 8.2 SAMPLE SIZE DETERMINATION

The target sample size of N=125 patient participants provides reasonable precision for estimating feasibility and acceptability measures in this pilot study. For instance, assuming 25% of participants initiate PrEP, the 95% confidence interval width for this proportion would be approximately 15.8%. This sample size is adequate for a pilot study aimed at informing the design of a future larger-scale trial rather than testing definitive efficacy hypotheses.

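### PrEP candidacy is discussed in the session but neither recorded nor analysed, so no stated rule keeps non-candidates out of the referral and uptake proportions, and the denominators in 8.2 and 8.3.2 differ

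*Combined protocol and SAP*

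**What the plan says.** **Target population.** The title in 1.1 is "PrEP Demonstration Project Among Women at Risk for HIV Infection". Section 2.1 gives the gap in knowledge as "how to facilitate effective access and use of PrEP for women at high risk for HIV infection" and speaks of PrEP-eligible women. The primary objective in 1.1 has no such qualifier: "To assess the feasibility, acceptability, and preliminary impact of an adapted patient-provider communication intervention on PrEP uptake among cisgender women".

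**Entry.** Section 4.1 admits HIV-uninfected (by self-report) adult cisgender women with English as their primary language, in care at a study site, who "report any sex with male partners in the past 6 months OR anticipate sexual activity with male partners in the next 6 months". No HIV risk factor or PrEP indication is required. Section 4.2 adds only case-by-case exclusion by the investigators.

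**Candidacy and referral.** In 5.1.1 the provider "uses the flip-book communication tool to guide discussion about HIV risk, PrEP candidacy, and prevention options". Then: "The session concludes with referral to PrEP services for interested participants or discussion of alternative risk-reduction strategies for those not interested in PrEP". The checklist in 5.2 documents which components of the tool were used.

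**Denominators.** Section 8.2 plans precision by "assuming 25% of participants initiate PrEP", with N=125 and a 95% interval about 15.8% wide. Section 8.3.2 divides referral acceptance by the women offered a referral, and uptake by eligible patients who were referred. It does not define *eligible* or *offered* for this purpose. No analysis in 8.3 uses candidacy or baseline risk.

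**The concern.** Entry is wider than the population named in the title and rationale, and the one step that could tell candidates from non-candidates leaves no planned record. For a woman with little HIV risk, not starting PrEP may be a proper result of the conversation. For a woman at risk, it may mean that the tool did not persuade her or that access failed. If both kinds of woman are in a denominator, the proportion alone cannot separate these explanations.

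This matters because 8.2 gives the purpose of the pilot as informing a larger trial. That trial will need an uptake rate with a known denominator. It will also need to know how precisely the rate was estimated, and the only precision figure given rests on a base that the analysis section does not use.

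**Working it through.** **1. Can any stated rule separate candidates from non-candidates?**

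| Step | Section | What decides it | Candidacy recorded or used? |
|---|---|---|---|
| Entry | 4.1, 4.2 | Recent or anticipated sex with a man; case-by-case exclusion | No |
| Session | 5.1.1 | Candidacy is discussed | Discussed; no definition given |
| Referral | 5.1.1 | Interest in PrEP | No |
| Checklist | 5.2 | Tool components used | No |
| Referral acceptance | 8.3.2 | Denominator: women offered a referral | Not tied to it |
| Uptake | 8.3.2 | Denominator: eligible patients referred | Not tied to it |
| Precision | 8.2 | Denominator: all 125 participants | No |

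The only eligibility that the protocol defines is that of 4.1, which carries no risk requirement. The two endings of the session in 5.1.1 both turn on interest; none is described for a woman judged not to be a candidate. So no stated rule does the separating.

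**2. The plan's own figure.** Inputs from 8.2: N=125, 25% uptake, 95% interval. The nearest whole count is 31 of 125 (24.8%). The exact (Clopper-Pearson) interval is 17.5% to 33.3%, width 15.8 points. The stated figure reproduces, so there is no arithmetic error. For comparison, the simple Wald width is 2 × 1.96 × √(0.25 × 0.75 / 125) = 15.2 points.

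**3. Dilution of a per-participant rate.** The documents give neither the share *c* of enrolled women who are candidates nor uptake *q* among them. Assume *q* = 25%, no uptake among non-candidates, and *c* from 20% to 100%. Uptake per enrolled woman is *c* × *q*. The last column is the exact 95% width if only candidates form the denominator, at the nearest feasible count.

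| *c* | Candidates of 125 | Uptake over all enrolled | Initiators / candidates | Width among candidates |
|---|---|---|---|---|
| 100% | 125 | 25% | 31/125 | 15.8 points |
| 80% | 100 | 20% | 25/100 | 17.8 points |
| 40% | 50 | 10% | 12/50 | 25.1 points |
| 20% | 25 | 5% | 6/25 | 35.8 points |

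Read the other way, 10% over all enrolled fits 0.20 × 50%, 0.40 × 25% or 1.00 × 10%: three quite different performances among candidates.

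**4. Does this carry over to 8.3.2?** Only in part. A non-candidate who is never offered a referral is in neither 8.3.2 denominator and dilutes nothing. One who is offered a referral and declines lowers referral acceptance. One who is referred and does not start PrEP lowers uptake, if she counts as eligible. The documents do not say how often either happens, so no figure can be put on it.

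**The case against.** The strongest reply is that the plan does not divide by all enrolled women. Both 8.3.2 proportions are conditioned on events during or after the session in which candidacy is discussed, and may already leave out most non-candidates. The all-participant base in 8.2 is offered only as an illustration of precision. This stands: the dilution table describes a per-participant rate, and mixing in the planned proportions is possible but not shown. What the reply does not supply is a rule, because *offered* and *eligible* remain undefined and referral turns on interest.

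Broad entry is also defensible. The tool exists to prompt a conversation about risk, so screening on risk beforehand would pre-empt part of the intervention. That stands too, and nothing here asks for a change to 4.1.

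Three stronger readings are tempting, and the documents do not support them:

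- *That 4.1 contradicts the objective.* The written primary objective says cisgender women. The at-risk wording is in the title and rationale.
- *That a low figure could not be interpreted at all.* Reasons for declining referral are to be tabulated (8.3.2), baseline sexual behaviours, substance use and partner violence are collected, and stage of change and an interview on PrEP decisions follow at 3 months (7.1). These help in part. However, 8.3.2 does not list reasons for not starting PrEP after referral, and no analysis by risk is planned.
- *That women who only anticipate sex are read out too early.* PrEP initiation is abstracted at 12 months as well as at 3 (7.1), although 8.3.2 does not say which reading defines uptake.

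**Conclusion.** The point holds as a gap in recording and in denominators. The candidacy outcome is neither recorded nor used, non-candidates are excluded from the 8.3.2 proportions by no stated rule, and 8.2 and 8.3.2 rest on different bases.

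The extent of dilution is unknown. Under the assumptions in the working, a per-participant rate could be anywhere from 25% down to 5% with the same uptake among candidates. This range shows sensitivity and does not predict the result; it reaches the 8.3.2 figures only so far as non-candidates are offered or referred. The firmer number concerns precision: 15.8 points applies only if all 125 women are the denominator. With 50, the exact width is about 25 points at about 25% uptake.

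A reader might infer that the entry criterion is wrong or that the planned proportions are known to be diluted. Neither is established. The change is still worth making, because it is cheap and because a candidacy outcome not recorded at the session may not be recoverable later.

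**What to change.** Leave 4.1 unchanged.

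1. **5.2:** add one field to the provider checklist for the outcome of the candidacy discussion, with a short definition of the categories.
2. **8.3.2:** for the post-intervention period, report referral acceptance and PrEP uptake among recorded candidates and among all enrolled women, alongside the planned proportions. Define *eligible* and *offered*.
3. **8.3.2:** describe uptake by baseline sexual-behaviour risk and by entry limb (recent sex, or anticipated sex only).
4. **8.2:** state that the 15.8-point width applies only with all 125 women in the denominator, and give the width for a smaller one (about 25 points for 50 women at about 25% uptake, exact interval).

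**Cost.** One field on a form already completed at each session and a few rows of descriptive output; no added visits or participants.

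**Limits.** The candidate subset has a wider interval. Candidacy is a provider's judgement made during the intervention and may depend on how the session went, so the rate among candidates is descriptive. The pre-intervention period has no such record, so the pre/post comparison keeps its planned denominator.

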### 4.2 EXCLUSION CRITERIA

Potential participants may be excluded if the Principal Investigators determine, on a case-by-case basis, that their participation would be medically unsafe, complicate interpretation of study findings, or otherwise interfere with achieving study objectives.

### 4.3 STRATEGIES FOR RECRUITMENT AND RETENTION

**Recruitment Methods:** Patient recruitment occurs through three approaches: (1) research assistant pre-screening of electronic medical records to identify potentially eligible patients with upcoming clinic visits; (2) recruitment flyers posted in clinic waiting areas; and (3) direct referral by healthcare providers at participating clinics.

Patients recruited through EMR pre-screening are formally screened during routine clinic visits. Patients recruited via flyers or provider referral either contact the research assistant directly using the phone number on flyers or provide permission to be contacted by study staff for telephone screening.

**Retention Strategies:** Participants receive compensation at each study visit (\$30 baseline, \$30 intervention, \$40 three-month follow-up). Reminder calls are conducted 24 hours before scheduled visits. Flexible scheduling options are provided for follow-up assessments, including in-person or telephone completion.

## 5 STUDY INTERVENTION

### 5.1 STUDY INTERVENTION(S) ADMINISTRATION

#### 5.1.1 STUDY INTERVENTION DESCRIPTION

The study intervention consists of a brief patient-provider communication session using a culturally adapted flip-book communication tool, optionally preceded by a 3-minute PrEP informational video. The intervention facilitates structured conversations about HIV risk assessment and PrEP as a prevention option.

During the intervention visit, participants may first watch the informational video about PrEP. The trained study provider then follows up on video content and uses the flip-book communication tool to guide discussion about HIV risk, PrEP candidacy, and prevention options. The session concludes with referral to PrEP services for interested participants or discussion of alternative risk-reduction strategies for those not interested in PrEP.

### 5.2 STUDY INTERVENTION COMPLIANCE

Intervention compliance is assessed through the providers' completion of content checklists, which document the use of communication tool components during each patient session. Providers complete brief feedback surveys weekly to assess intervention delivery fidelity and implementation challenges.

## 6 STUDY INTERVENTION DISCONTINUATION AND SUBJECT DISCONTINUATION/WITHDRAWAL

### 6.1 SUBJECT DISCONTINUATION/WITHDRAWAL FROM THE STUDY

Subjects are free to withdraw from participation in the study at any time upon request.

An investigator may discontinue or withdraw a subject from the study for the following reasons:

- Significant study intervention non-compliance
- If any clinical adverse event (AE), laboratory abnormality, or other medical condition or situation occurs such that continued participation in the study would not be in the best interest of the subject

Subjects who withdraw or are discontinued from the study will not be replaced, as this is a pilot feasibility study.

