### 8.3.2 ANALYSIS OF THE PRIMARY EFFICACY ENDPOINT(S)

**Intervention feasibility:** Feasibility will be assessed using descriptive statistics (i.e., counts and proportions) for: recruitment numbers (number of participants screened), enrollment rate (proportion of eligible participants consenting), participant retention (proportion completing 3-month follow-up), PrEP referral acceptance rate (proportion accepting referral among those offered), and intervention delivery completion rate (proportion receiving complete intervention). Reasons for non-participation, referral decline, and incomplete intervention delivery will be summarized using frequency distributions and percentages.

**Intervention acceptability.** Acceptability will be assessed using descriptive statistics (mean and standard deviation) for CSQ-8 scores among patient participants. Missing item responses will be handled according to each instrument's scoring guidelines.

**PrEP uptake changes.** PrEP uptake rates will be compared between the 7-month pre-intervention period and the post-period using binomial logistic regression. Time period (pre-intervention vs. post) will serve as the primary predictor. Uptake proportions (i.e., patients who initiate PrEP over eligible patients referred) and 95% confidence intervals will be calculated to estimate the change in uptake rates between periods.

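### Allowing withdrawal for intervention non-compliance lets an investigator's decision lower 3-month retention, a primary feasibility outcome, and loses follow-up on women whose session went badly

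*Combined protocol and SAP*

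**What the plan says.** Section 6.1 introduces its list of grounds with "An investigator may discontinue or withdraw a subject from the study for the following reasons". The first ground is "Significant study intervention non-compliance"; the second is a safety ground. The section does not say what makes non-compliance significant or whose non-compliance counts. Withdrawn women are not replaced.

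Section 5.2 is the only place where compliance is given a measure: "Intervention compliance is assessed through the providers' completion of content checklists, which document the use of communication tool components during each patient session". The protocol has no participant-level measure of compliance.

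Section 8.3.2 analyses several feasibility outcomes, which the synopsis (1.1) lists as primary. Two matter here: "participant retention (proportion completing 3-month follow-up") and "intervention delivery completion rate (proportion receiving complete intervention"). The same section adds "Reasons for non-participation, referral decline, and incomplete intervention delivery will be summarized using frequency distributions and percentages". It defines uptake as "patients who initiate PrEP over eligible patients referred".

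Sections 1.2 and 7.1 schedule an assessment and a qualitative interview at 3 months, and chart abstraction of PrEP initiation and visit attendance at 3 and 12 months. The protocol does not say whether abstraction continues after withdrawal, what the retention denominator is, or how withdrawn women are analysed.

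**The concern.** In this pilot, an incomplete or missed session is a result. The plan promises to count such sessions and explain them. Section 6.1 makes what appears to be the same event a reason to end a woman's participation.

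Two things are at stake. First, retention should describe what the women did. Once an investigator can end participation on this ground, it also reflects how often the ground was used. Second, the women removed would be those whose 3-month data could show what follows when delivery goes wrong, in a study that refines its tool in iterative cycles (section 3.1).

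The ground also serves little evident purpose. The intervention is one brief session with an optional video (section 5.1.1), after which only data collection remains, so there is no continuing regimen to comply with. Missed visits are already covered by section 6.2, which requires at least three telephone attempts before a woman is declared lost. Section 6.1 has no such safeguard.

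**Working it through.** **The plan's own figure.** Section 8.2 gives a 95% interval width of about 15.8% for 25% uptake with N = 125.
- Simple normal interval: 2 × 1.96 × √(0.25 × 0.75 / 125) = 0.152.
- Exact (Clopper-Pearson) interval for 31/125: 17.5% to 33.3%, a width of 15.8 points.

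The figure reproduces with the exact interval and is not in dispute. It uses all 125 women and makes no allowance for withdrawal.

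**Retention.** Inputs: N = 125 (section 8.2); no replacement (section 6.1); k = number withdrawn for non-compliance before month 3. The documents give no value for k, so 5, 10 and 15 are assumed. A withdrawn woman cannot complete the 3-month follow-up, so the highest possible all-enrolled retention is (125 − k)/125.

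To see the effect at a plausible retention level, let r be the completion rate without the rule, assumed to be 90% or 80% and the same for withdrawn women as for the rest. All-enrolled retention is then r × (125 − k)/125.

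| k | Maximum retention | r = 90% becomes | r = 80% becomes |
|---|---|---|---|
| 5 | 120/125 = 96% | 86.4% | 76.8% |
| 10 | 115/125 = 92% | 82.8% | 73.6% |
| 15 | 110/125 = 88% | 79.2% | 70.4% |

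If the withdrawn women would have completed at some other rate q, the fall is k × q/125. It is zero if none would have completed (q = 0), and 4, 8 or 12 points if all would have (q = 1).

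The denominator is not stated. If withdrawn women were left out of it, 90% would stay at 90%, but the figure would no longer describe everyone enrolled.

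**Data lost.** The 3-month assessment and interview need the woman's participation and end with withdrawal. The charts could still be read, but the plan is silent on whether they will be.

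**Uptake.** Let R be the women referred and x the initiators among them. Let j be the women referred, then withdrawn and excluded, and i the initiators among those j. Uptake moves from x/R to (x − i)/(R − j). It rises only if i/j is below x/R, and does not change if the two are equal. The documents give no value for R, j or i. The 25% in section 8.2 is a proportion of participants, not of women referred, so it cannot be used here. A woman whose session stopped before referral is outside this denominator whatever section 6.1 says.

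**The case against.** The strongest reply is that an ordinary reader takes section 6.1 to mean the woman's own conduct, such as refusing or repeatedly missing the session. On this view the section 5.2 checklist only monitors delivery, and nothing makes it a trigger for withdrawal. The ground is discretionary and limited to significant cases, so it may never be used. Delivery completion is settled at the session, and the satisfaction questionnaire is completed straight after it, so neither is lost through a withdrawal prompted by that session. Reasons for incomplete delivery will be reported. On this argument, defining the term and the denominators would be enough.

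Much of this stands. A reader might infer that women will be withdrawn because their provider delivered the session poorly. That comes from joining sections 5.2 and 6.1, which the protocol does not join; its wording leaves this open but does not state it. The link from the checklist to a complete intervention in 8.3.2 is likewise a reasonable reading, not a stated rule. The frequency is unknown.

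The retention point does not depend on any of this. Even if only the woman's own conduct counts, a refused or missed session is a feasibility finding, and she could still be followed to month 3. A definition would limit how often the rule is used, but each use would still end follow-up that could have continued.

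**Conclusion.** The point holds for retention and for the 3-month data. Every use of the ground before month 3 removes a possible completer by an investigator's decision and loses her assessment and interview. With 5, 10 or 15 of 125 withdrawn, all-enrolled retention cannot exceed 96%, 92% or 88%. Those counts are assumptions, and the actual fall depends on how many of the women would otherwise have completed.

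Two stronger conclusions are tempting but unsupported. One is that the rule inflates PrEP uptake. No section says withdrawn women leave the uptake analysis, and its denominator is women referred, so the most that can be said is that uptake could shift for women referred, then withdrawn and excluded, by an amount the documents do not allow to be sized. The other is that chart outcomes will be lost. The plan is silent on this, so they may be. That silence still matters, because it leaves the handling of withdrawn women to be decided after results are seen.

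The change should be made: it protects a primary outcome and costs very little.

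**What to change.** In section 6.1, remove non-compliance as a ground for withdrawal from the study. Leave voluntary withdrawal and the safety ground unchanged.

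Add a statement that women with an incomplete or missed session stay in the study for the 3-month assessment and for chart abstraction at 3 and 12 months, unless they withdraw consent.

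In section 8.3.2, state that retention is calculated over all enrolled women, including these, and that any of them who were referred stay in the uptake denominator.

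The cost is one deleted bullet and a few added lines. It needs no visits or staff beyond those planned, and it concerns study follow-up and analysis, not anyone's care.
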